3.5.3 Contrast Sensitivity

Contrast sensitivity was assessed at the Month 9, 12, 18, 24, 36, 48, and 60 visits.

Contrast sensitivity (LogCS) will be measured using the Pelli-Robson chart. Measurements for each eye and both eyes will be taken.

The arithmetic mean of the multiple observations at baseline will be used as the baseline value.

Achievement of any visual improvement above the test-retest variation (yes/no) as measured by the contrast sensitivity (LogCS) will be summarized for study eye and the difference between eyes (study eye minus fellow eye) for all participants.

Summary statistics of the contrast sensitivity observed values and change from baseline by study eye and assessment by distance at testing for all participants will be presented.

The difference between the study eye and the fellow eye of contrast sensitivity, the difference at each visit, along with its change from baseline data, will be summarized. At each post-baseline visit, the change from baseline in the difference between the study eye and the fellow eye will be tested by a nonparametric Wilcoxon signed rank test as the primary method. The p-value from the t-test and the Shapiro-Wilk Normality test will also be provided.

All contrast sensitivity observed values will be listed.

In-text displays:

- Average Plot of Contrast Sensitivity Change from Baseline Over Time
- Individual Plot of Contrast Sensitivity Change from Baseline Over Time

3.5.4 Reading Speed

Reading speed was assessed at the Month 9, 12, 18, 24, 36, 48, and 60 visits.

Reading ability, including reading distance (cm), reading acuity (LogMAR), maximum reading speed (words/minute), and critical print size (LogMAR) will be assessed with MNRead and International Reading Speed Texts.

The arithmetic mean of the multiple observations at baseline will be used as the baseline value.

Achievement of visual improvement above the test-retest variation (yes/no) as measured by maximum reading speed will be summarized for study eye and difference between eyes (study eye minus fellow eye) for all participants.

The number and percentage of participants with a reading distance of 40 cm or 25 cm will be presented for the study eye for all participants.

Summary statistics of the maximum reading speed observed values and change from baseline by study eye for all participants will be presented.

The difference between the study eye and the fellow eye of reading speed (words/minute), the difference at each visit along with its change from baseline data will be summarized. At each post-baseline visit, the change from baseline in the difference between the study eye and the fellow eye will be tested by nonparametric Wilcoxon signed rank test as the primary method. The p-value from the t-test and the Shapiro-Wilk Normality test will also be provided.

All reading speed data will be listed.

In-text displays:

- Average Plot of Maximum Reading Speed Change from Baseline Over Time
- Individual Plot of Maximum Reading Speed Change from Baseline Over Time

3.5.5 Quality of Life

3.5.5.1 Impact of Visual Impairment (IVI) Questionnaire

IVI was assessed at the Month 12, 24, 36, 48, and 60 visits.

The IVI quality of life questionnaire queries the level of restriction of participation in common daily experiences. For this study, there will be 2 sets of questionnaires. The adults will complete a 28-item questionnaire (IVI-A) and the children will complete a 24-item questionnaire (IVI-C).

For adults, the questionnaire covers a broad range of issues in 3 separate domains of functioning. The domains and the items that they contain are:

- Reading and accessing information domain contains items 1, 3, 5, 6, 7, 8, 9, 14, 15. Items 1, 3, and 5 to 9 will be rated on a 5-level scale (0 = a lot, 1 = a fair amount, 2 = a little, 3 = not at all, and 8 = don't do this for other reasons). Items 14 and 15 will be rated on a 4-level scale (0 = a lot, 1 = a fair amount, 2 = not at all, and 8 = don't do this for other reasons).
- Mobility and independence domain contains items 2, 4, 10, 11, 12, 13, 16, 17, 18, 19, 20. Items 2, 4, and 10 to 13 will be rated on a 5-level scale (0 = a lot, 1 = a fair amount, 2 = a little, 3 = not at all, and 8 = don't do this for other reasons). Items 16 to 20 will be rated on a 4-level scale (0 = a lot, 1 = a fair amount, 2 = a little, and 3 = not at all).
- Emotional well-being domain contains items 21 to 28. These items will be rated on a 4-level scale (0 = a lot of the time, 1 = a fair amount of time, 2 = a little of the time, and 3 = not at all).

Domain scores will be calculated by first reversing scores (0, 1, 2, 3) to (3, 2, 1, 0) to allocate the better IVI scores to the less impaired. The higher the score, the worse the quality of life. Category 8 (don't do this for other reasons) will be excluded from the domain scores derivation as it does not relate to impairment. The domain scores are calculated by summing the reversed scores across relevant items within each domain.

Domain scores will be calculated for each participant at baseline and any other assessments where data is captured. There are no domains specified on the children's version of the questionnaire, so domain scores will not be calculated.

The total IVI score represents the overall impact of vision impairment on an individual's participation in daily activities. It is obtained by summing the domain scores (emotional well-being, reading/accessing information, and mobility/independence).

Summaries will be reported for adults, with summary statistics of the calculated total scores per domain and change from baseline summarized by assessment and dose level.

All IVI data will be listed.

In-text displays:

- Histogram of IVI Questionnaires for Adults Total score
- · Histogram of IVI Questionnaires for Children Part 1
- Histogram of IVI Questionnaires for Children Part 2

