3 STATISTICAL METHODOLOGY

3.1 General Considerations

3.1.1 Definition of Baseline

The baseline values of MGT006 and MGT012 final analyses will be used for the MGT007 final analyses.

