3.1.5 Data Presentations

All data will be summarized by dose level. For each study, a separate study-specific total should summarize all dose levels for that study. In addition, an overall column that includes all participants of both studies should also be presented.

The following table summarizes the number of dosed participants and the associated dose levels in studies MGT006 and MGT012.

Dose Level (vg/mL)	Number of MGT006 Participants Dosed	Number of MGT012 Participants Dosed
	3	3
	12	3
	3	NA
	5	5
Study Total	23	11

Unscheduled measurements and repeat measurements not due to technical failure will be listed but not summarized. If a repeat measurement is due to a technical failure, it will be included in the summaries.

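### Adult IVI reading and mobility scores are plain sums with category 8 left out, so switching to or from that answer moves the score by 1 to 3 points per item with no change in visual impairment

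*SAP*

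**What the plan says.** SAP 3.5.5.1 scores the 28-item adult questionnaire in three domains: reading (9 items), mobility (11) and emotional well-being (8). Codes 0, 1, 2, 3 are reversed to 3, 2, 1, 0, and a higher score means worse quality of life. Category 8 "will be excluded from the domain scores derivation as it does not relate to impairment". The score is then a plain sum: "The domain scores are calculated by summing the reversed scores across relevant items within each domain". The total is the sum of the three domain scores.

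Category 8 is an option on all nine reading items and on mobility items 2, 4 and 10 to 13. Reading items 14 and 15 have a shorter list, in which *not at all* is coded 2 rather than 3.

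The planned adult output is "summary statistics of the calculated total scores per domain and change from baseline summarized by assessment and dose level", plus a histogram of the total score. SAP 3.1.1 takes baseline from the parent studies: "The baseline values of MGT006 and MGT012 final analyses will be used for the MGT007 final analyses".

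Neither document gives a minimum number of scored items, a proration rule or a rule for blank IVI items. The EQ-5D-5L index does have a rule (SAP 3.5.5.2): it needs all five dimensions.

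**The concern.** The SAP's reason for leaving out category 8 is that it carries no information about impairment. In an unadjusted sum, however, leaving an item out gives it 0 points, which is the best possible answer on the items coded 0 to 3. The rule thus scores as no impairment an answer that it has just declared uninformative.

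Follow-up runs to Month 60, with IVI at Months 12, 24, 36, 48 and 60. If a participant stops or starts an activity for reasons unrelated to vision, the change from baseline moves.

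Quality of life is the third secondary outcome, and IVI is one of its two instruments. SAP section 4 drops full-field and pattern ERG from analysis, so quality of life is one of two secondary outcomes still analysed. Protocol 5.9.3.2 also intends to relate quality of life to clinical observations. Dose groups are small, so a few switches can move a group mean.

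**Working it through.** The SAP gives no IVI score range to reproduce. As a consistency check, the listed items number 9 + 11 + 8 = 28, which matches the stated length of the adult form.

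**Items open to the shift** (SAP 3.5.5.1)
- Reading: 1, 3, 5 to 9, 14, 15 = 9 of 9.
- Mobility: 2, 4, 10 to 13 = 6 of 11.
- Emotional well-being: 0 of 8.
- In all 15 of 28. Without items 14 and 15, 13 items, all coded 0 to 3.

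**Change in score when one item moves to category 8.** Reversed score = 3 − code, and category 8 adds 0, so the change is −(3 − code).

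| Answer before | 13 items coded 0–3 | Items 14, 15 (stated reversal) |
|---|---|---|
| *a lot* | −3 | −3 |
| *a fair amount* | −2 | −2 |
| *a little* | −1 | not offered |
| *not at all* | 0 | −1 |

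The reverse move has the opposite sign. For items 14 and 15 the stated reversal turns *not at all* into 3 − 2 = 1, so a skipped item scores better than no difficulty. This offset shifts score levels but cancels in change scores when both items are answered at both visits.

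**One participant.** All 11 mobility items at *a fair amount* give 11 × 2 = 22. With one item moved to category 8 the sum is 10 × 2 = 20, an apparent improvement of 2/22 = 9%. A prorated score is 20/10 × 11 = 22, unchanged.

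**Group mean.** SAP 3.1.5 lists groups of 3, 5 and 12 dosed participants per dose level and study. One adult moving one item from *a lot* to category 8 shifts the mean change by 3/n: 1.0 point for n = 3, 0.6 for n = 5 and 0.25 for n = 12. The shift is larger where fewer adults have data.

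**Range under an assumption.** The documents give no switching frequency. Assume that each of the 13 items switches independently with probability p, and that the reversed score x is spread evenly over 0 to 3, so E[x] = 1.5 and E[x²] = 3.5. With k items, two-way switching in equal measure adds an SD of √(k × p × 3.5) per participant. If all switches go to category 8, the mean shift is −k × p × 1.5.

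| p | Reading (k = 7): SD; shift | Mobility (k = 6): SD; shift | Total (k = 13): SD; shift |
|---|---|---|---|
| 2% | 0.70; −0.21 | 0.65; −0.18 | 0.95; −0.39 |
| 5% | 1.11; −0.53 | 1.02; −0.45 | 1.51; −0.98 |
| 10% | 1.57; −1.05 | 1.45; −0.90 | 2.13; −1.95 |

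The domain columns matter most, because change from baseline is planned by domain.

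**Theoretical ceiling.** If all 15 items moved from *a lot* to category 8, the total would fall by 15 × 3 = 45 of 28 × 3 = 84 points (53.6%). With items 14 and 15 scored 0 to 2 it would fall by 13 × 3 + 2 × 2 = 43 of 26 × 3 + 2 × 2 = 82 (52.4%). This shows the reach of the rule and is not a realistic case.

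**The case against.** The strongest reply concerns weight. IVI is an untested, adults-only descriptive summary. The signed rank tests and t-tests apply to acuity, contrast sensitivity and reading speed. All IVI data are listed, so with 34 dosed participants a reader could find a switch to category 8. The EQ-5D index and EQ-VAS are unaffected. The frequency and net direction of switches are unknown, and the documents give no between-participant SD or meaningful change against which to judge 1 to 2 points. All of this stands, and it limits the importance of the point. It does not remove the error, because a listing does not correct a summary table.

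Proration is also imperfect. The mobility example comes out exactly because every item has the same answer. Take reading with one item at *a lot* and eight at *a little*, a sum of 3 + 8 = 11. If the *a lot* item moves to category 8, the plain sum falls to 8 (−3) and the prorated score to 8/8 × 9 = 9 (−2). The shift is reduced but not removed.

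SAP section 5 refers to separate programming specifications, which are not available here. They could hold a rule for blank items, but the SAP itself specifies a plain sum. The coding of items 14 and 15 may be a transcription slip.

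**Conclusion.** The concern holds. Followed exactly, the stated rule produces changes in the adult reading and mobility scores, and in the total, that do not reflect visual impairment: 1 to 3 points for each switch between a difficulty level and category 8. Emotional well-being and the children's data are not affected.

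The mechanism and the 3/n shifts follow from the SAP alone. The SDs and mean shifts rest on the assumed 2% to 10% switching, independence between items and evenly spread answers. The actual size is unknown until category-8 answers are counted. Because the summary is descriptive, the point should be corrected but does not threaten the primary objective.

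**What to change.** - Score each domain as the mean of its scored items, or that mean times the number of items in the domain. Set a prespecified minimum number of scored items; half is a possible choice, offered here as a proposal.
- Build the total in the same way, and apply the same rule to blank items.
- Check items 14 and 15 against the CRF code list, and reverse them so that *not at all* becomes 0.
- Rederive the IVI baseline from parent-study item data by the same rule, and state this as an exception to SAP 3.1.1. Otherwise baseline and follow-up could be on different scales.
- Report the number of category-8 answers by domain and visit, and keep the plain sum as a supportive display.

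The cost is SAP wording, one derivation and the rederived baseline; no new data are needed. The new scores will differ from the parent-study tables, and the supportive plain sum keeps the link. Proration assumes that unscored items resemble scored ones, which is why the minimum is needed.

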3.5.5.2 EQ-5D-5L and EQ-5D-Y

EQ-5D-5L and EQ-5D-Y were assessed at Month 12, 24, 36, 48, and 60 visits.

The EQ-5D is a standardized measure of health status. The EQ-5D-5L questionnaire will be completed by adults, while EQ-5D-Y will be completed by children.

The 5 dimensions of both questionnaires are:

- Mobility
- Self-care
- Usual activities
- Pain/discomfort
- Anxiety/depression

Each of the dimensions of EQ-5D-5L has 5 levels:

- Level 1: indicating no problems
- · Level 2: indicating slight problems
- · Level 3: indicating moderate problems
- Level 4: indicating severe problems
- · Level 5: indicating extreme problems

A total of 3125 health states are possible. Each state is referred to in terms of a 5-digit code. For example, state 11111 indicates no problem on any of the 5 dimensions, while state 12345 indicates no problems with mobility, slight problems with self-care, moderate problems with doing usual activities, severe pain or discomfort, and extreme anxiety or depression.

Only one response should be provided for each dimension, and missing values will be coded as 9. If 2 levels are selected for a dimension, the dimension will be treated as missing.

For participants who complete the EQ 5D 5L questionnaire, the health states will be converted into a single index value for each participant that has complete data for the 5 dimensions. The conversion will be done using the crosswalk value sets provided by the EuroQol research foundation (Euroqol.org, 2019). The crosswalk value sets for the UK will be used for UK participants and the crosswalk value sets for the US will be used for US participants.

Each of the dimensions of EQ-5D-Y has 3 levels:

- · Level 1: indicating no problems
- Level 2: indicating moderate problems
- Level 3: indicating extreme problems

Due to the absence of a mapping scale for the youth questionnaire, the 5 dimensions will be analyzed individually.

Both questionnaires also contain a visual analog scale (EQ-VAS) where the participant is asked to rate their health state on a 0 to 100 scale between the worst health imaginable (0) and best health imaginable (100).

For EQ-5D-5L and EQ 5D Y separately, the number of participants and percentage of participants who reported problems at each level for each dimension will be presented. The summaries will be presented by dose level in the dose escalation and dose expansion phase and for all participants.

In addition, a single index will be derived for each participant who completed the EQ 5D-5L questionnaire. The derived EQ 5D index value and the change from baseline will be summarized.

The EQ-VAS observed and changes from baseline data will be summarized for the EQ-5D-5L and EQ-5D-Y questionnaires separately.

All EQ 5D-5L and EQ 5D Y data will be listed.

In-text displays:

- EQ-5D-5L Individual Dimensions: Percentage of Subjects Reporting Problems at Baseline and End of Study
- EQ-5D-Y Individual Dimensions: Percentage of Subjects Reporting Problems at Baseline and End of Study

3.5.6 Multiplicity

No adjustments for multiple comparisons will be made.

4 CHANGES FROM PROTOCOL-SPECIFIED ANALYSIS

- Samples for immunological response will be stored and will not be analyzed at this time.
- Videos of photoaversion test will be stored for future use and will not be analyzed at this time.
- Data from the following assessments will not be analyzed:
 - o computerised (achromatic) spatial contrast sensitivity function tests
 - Colour Vision
 - Octopus Perimetry
 - Optical Coherence Tomography
 - Photoaversion
 - o Full field electroretinography
 - Pattern electroretinography
 - o Adaptive optics imaging
 - o Full Field Stimulus Testing

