#### 4.2 Rationale

There is currently no effective treatment available for most hereditary retinal disorders including achromatopsia. This condition is characterised by absent (or markedly reduced) cone function resulting in profound reduction in visual acuity, complete lack of (or markedly reduced) colour vision, marked Photoaversion and nystagmus. The *CNGB3* gene encodes the beta subunit of the cone photoreceptor-specific cGMP-gated cation channel and the CNGA3 gene encodes the alpha subunit, both of which are critical for cellular responses to light. Absence of either the beta or the alpha subunit results in absent/extremely poor cone function and hence very poor daylight vision. Although loss of cone photoreceptor cells over time may occur in a limited number of patients, the rate of cell death appears to be very slow, resulting in retinas containing surviving but non-functioning cones. Improvement of cone function by provision of *CNGB3* or *CNGA3* (as appropriate) could provide a clear, rapid and reliable measure of outcome. Furthermore, the relatively non-progressive nature of achromatopsia, with extended survival of cone photoreceptors, means that the window of opportunity for effective intervention by gene supplementation may extend into adulthood.

However, since achromatopsia results in marked visual impairment from birth, associated abnormal development of physiological cone-dependent neuronal circuits, including that of the visual cortex, may limit the potential for older individuals to benefit from therapeutic restoration of retinal function. Since visual cortical plasticity is known to be greater in younger children, we will recruit children once an acceptable safety profile has been defined in adults. Older participants might benefit with relief from photoaversion even if limited cortical plasticity affects the potential for improved acuity or colour vision.

The purpose of the CNGB3 and CNGA3 interventional trials and this longer term follow up study is to determine the safety and potential efficacy of the vector AAV8-hCARp.hCNGB3 and AAV8-hG1.7p.coCNGA3 respectively.

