#### 5.4.1.1.2 Functional and Participant-Related Outcome assessments

Where possible the participant will complete an age appropriate Impact of Visual Impairment (IVI) vision-specific quality of life questionnaire, and EQ5D-5L questionnaire.

Reading ability including reading acuity, maximum reading rate, and critical print size will be assessed with MNRead and International Reading Speed Texts.

The degree of light sensitivity (photoaversion) will be investigated in 2 ways (i) Objectively by measurement of palpebral aperture narrowing in response to gradually increasing light intensity and (ii) Subjectively by participant reported symptomatology.

Best-corrected ETDRS visual acuity will be measured in each eye. Contrast sensitivity will be measured using the Pelli-Robson chart or computerised (achromatic) spatial contrast sensitivity function tests.

Colour vision will be assessed comprehensively using plate tests and computerised tests probing colour discrimination along all 3 axes of colour and other testing methods may also be used as appropriate.

Retinal sensitivity will be determined using static perimetry and full field stimulus testing (FST) where available.

Full-field electroretinography (ERG), pattern ERG (PERG) will be performed according to the International Society for Clinical Electrophysiology of Vision (ISCEV) standards to assess both generalised retinal (rod and cone systems) and isolated macular function. Modified ISCEV protocols may be necessary in young children using internationally recognised modified protocols. ERG assessments may be performed under general anaesthesia if considered appropriate. ERG data will be analysed and interpreted by dedicated full-time Clinical Visual Electrophysiology Consultants at Moorfields Eye Hospital, UK, with extensive experience and who are directly involved in determining ISCEV standards.

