2.2.3 Sample Size Determination

This is a long-term follow-up study; therefore, there is no formal sample size calculation.

23 and 11 participants were randomized and dosed in the MGT006 and MGT012 studies, respectively. All participants enrolled in the MGT006 and MGT012 studies were invited to participate in this follow-up study.

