2.3.2 Secondary Endpoints

The secondary outcomes are measures of the efficacy of the ATIMP; these will be performed on an individual participant basis and will be descriptive in nature:

- 1) Any improvements in visual function from baseline that are greater than the test-retest variation and are sustained for at least two consecutive assessments.
- 2) Any improvement in retinal function from baseline that is greater than test-retest variation and measurable by electrophysiology (pattern ERG, or full-field ERG).
- Quality of life will be measured by the Impact of Visual Impairment (IVI) questionnaire and the EQ5D-5L.

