3.5.2 Visual Acuity

Visual acuity was assessed at the Month 9, 12, 18, 24, 36, 48, and 60 visits.

4 meter refraction of the sphere, cylinder, and axis of each eye will be measured. Best-corrected ETDRS visual acuity will be measured.

The arithmetic mean of the multiple observations at baseline will be used as the baseline value.

Achievement of visual improvement above the test-retest variation (yes/no) as measured by a number of ETDRS letters will be summarized for study eye and the difference between eyes (study eye minus fellow eye) for all participants.

The 4-meter refraction (sphere, cylinder, and axis) observed values will be summarized for the study eye for all participants.

Summary statistics of all ETDRS visual acuity observed values and the change from baseline by study eye and the difference between eyes (study eye minus fellow eye) for all participants will be presented.

The difference between the study eye and the fellow eye of ETDRS letters, the difference at each visit, along with its change from baseline data, will be summarized. At each post-baseline visit, the change from baseline in the difference between the study eye and the fellow eye will be tested by a nonparametric Wilcoxon signed rank test as the primary method. The p-value from the t-test and the Shapiro-Wilk Normality test will also be provided.

All visual acuity data will be listed.

In-text displays:

- Average Plot of BCVA (ETDRS Letters) Change from Baseline Over Time
- Individual Plot of BCVA (ETDRS Letters) Change from Baseline Over Time

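### SAP section 4 drops four visual-function tests, including photoaversion, without a reason, while secondary endpoint 1 still covers visual function as a whole

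*SAP*

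**What the plan says.** SAP 2.3.2 carries secondary endpoint 1 over from Protocol 5.5.2 unchanged: "Any improvements in visual function from baseline that are greater than the test-retest variation and are sustained for at least two consecutive assessments". Protocol 5.9.3.2 adds that measures will be reported individually and also as the proportion of participants who satisfy the criteria.

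SAP 3.5.2 to 3.5.4 define improvement analyses for ETDRS acuity, Pelli-Robson contrast sensitivity and maximum reading speed. SAP section 4 then says of photoaversion, "Videos of photoaversion test will be stored for future use and will not be analyzed at this time". A second item reads "Data from the following assessments will not be analyzed", and its list includes colour vision, Octopus perimetry, photoaversion and FST. No reason is attached to any of them.

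Protocol 4.2 says: "Older participants might benefit with relief from photoaversion even if limited cortical plasticity affects the potential for improved acuity or colour vision". Protocol 5.4.1.1 puts photoaversion testing and static perimetry among the tests done in all participants. Protocol 5.4.1.1.2 measures photoaversion objectively, by palpebral aperture, and "Subjectively by participant reported symptomatology". A footnote to the schedule in Protocol 5.6 confirms that both the device and questionnaires are used.

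**The concern.** The wording of endpoint 1 promises more than the SAP delivers. A participant whose only sustained gain is in light sensitivity, colour discrimination, perimetric sensitivity or FST threshold would appear in no planned summary, although the endpoint's wording includes that gain.

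The omission is not neutral with respect to the protocol's own reasoning. For older participants the rationale raises the possibility that acuity and colour vision change little while photoaversion eases. The SAP keeps acuity and drops photoaversion. The retained tests also receive visit-by-visit Wilcoxon tests on the study-minus-fellow-eye difference, while the dropped tests receive no summary at all.

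At stake is what the report can say about visual function, and whether a reader can tell why outcomes that were measured are missing from it.

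**Working it through.** There is no planned sample size or power figure to reproduce ("This is a long-term follow-up study; therefore, there is no formal sample size calculation"). The check sets the protocol's tests beside the SAP's analyses.

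**Step 1. Tests.** The visual-function tests are those described in Protocol 5.4.1.1.2. Their status is from Protocol 5.4.1.1 and their visits from the schedule in Protocol 5.6.

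| Test | Status in protocol | Scheduled visits | SAP |
|---|---|---|---|
| Acuity | all participants | 7 | analysed, 3.5.2 |
| Contrast sensitivity | all participants | 7 | analysed, 3.5.3 (Pelli-Robson) |
| Reading | unless not possible | 7 | analysed, 3.5.4 |
| Photoaversion | all participants | 5 | excluded |
| Static perimetry | all participants | 7 | excluded |
| Colour vision | unless not possible | 7 | excluded |
| FST | unless not possible | 7 | excluded |

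Three of seven are analysed and four of seven are not. I take the SAP's Octopus perimetry to be the protocol's static perimetry; the SAP contains no other perimetry analysis. Expected completeness does not explain the split: two tests required in everyone are out, and one done only where possible is in.

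**Step 2. Scheduled test-visits per participant.**
- Analysed: 3 × 7 = 21.
- Not analysed: 5 + 7 + 7 + 7 = 26.
- Share not analysed: 26 / (21 + 26) = 26/47 = 55%.

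**Step 3. Participants.** SAP 2.2.3: "23 and 11 participants were randomized and dosed in the MGT006 and MGT012 studies, respectively", so 23 + 11 = 34. The dose table in SAP 3.1.5 agrees: 3 + 12 + 3 + 5 = 23 and 3 + 3 + 5 = 11. The ceilings are:
- photoaversion: 34 × 5 = 170 participant-visits;
- colour vision, perimetry and FST: 34 × 7 = 238 participant-visits each.

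These are upper bounds. The 34 were dosed in the parent studies and then invited; they are not necessarily all enrolled here. Colour vision and FST depend on co-operation and equipment, FST stops after Month 12 if responses remain undetectable, and children do only the tests they can perform reliably.

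**Step 4. What endpoint 1 can count.** SAP 3.5.1 classes a participant as improved for the relevant test. With analyses for three tests only, improvement can be recorded for those three only. Nothing in SAP 2.3.2 or 3.5.1 limits endpoint 1 to them.

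**Step 5. Does the video explanation cover photoaversion?** No. The deferral of the videos concerns stored recordings. Photoaversion appears again, as its own item, in the list of data not to be analysed, so the questionnaires are excluded too, and they need no video reading. The qualifier that leaves later analysis open is attached to the videos and the immunology samples, not to that list.

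The same list removes both ERG tests, which bears on secondary endpoint 2. That is a separate matter and is not counted here.

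**The case against.** Several points on the other side stand.

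- **No overall verdict is defined.** A reader might infer that the study would declare no improvement in visual function. The SAP classifies improvement test by test and sets no any-test composite, so its outputs support only test-specific statements. The defect is the mismatch between the endpoint and its analysis, not a wrong verdict already built in.
- **The rationale is tentative.** A reader might infer that the protocol predicts relief from photoaversion. It says only that older participants might benefit.
- **Data-driven exclusion is not shown.** A reader might infer selection after sight of results, because the study is open-label and the SAP uses the past tense ("Visual acuity was assessed at the Month 9, 12, 18, 24, 36, 48, and 60 visits"). The tense shows that visits took place, not that results guided the choice; the quality-of-life sections, which are retained, use it as well. SAP section 1 says the plan will be finalised before database lock. The contents page still lists a photoaversion section with a dead bookmark, which could be left over from a template.
- **The change is disclosed.** It appears in the section meant for changes, and SAP section 5 says all available data will be listed. But disclosure without a reason does not align the endpoint with its analysis, and a listing is neither a summary nor the proportion described in Protocol 5.9.3.2.
- **Scoring is incomplete.** The documents define no summary variable for colour vision, the photoaversion questionnaires or perimetry, and do not show test-retest data for every dropped test. Definitions written now come after visits have occurred. This limits what the fix can ask for.
- **Efficacy is secondary, exploratory and descriptive.** The primary safety outcome is untouched.

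**Conclusion.** The point holds in a limited form. Secondary endpoint 1 is broader than its analysis: four of seven visual-function tests, and up to 55% of scheduled visual-function test-visits per participant, have no planned summary and no stated reason. One of the four is the domain the protocol names as a possible benefit for older participants. A benefit confined to a dropped test would not be summarised.

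This rests on two readings: that the seven tests in Protocol 5.4.1.1.2 make up visual function (neither document gives a closed list, and the protocol describes perimetry and FST as measures of retinal sensitivity), and that the extracted schedule table is correct. If perimetry and FST are set aside, photoaversion and colour vision still lack an analysis, so the mismatch remains. How many participants might improve only in a dropped test cannot be derived from the documents, and the conclusion does not need that number.

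**What to change.** 1. Take the photoaversion questionnaires and static perimetry off the SAP section 4 exclusion list, and colour vision and FST where a score was recorded. Summarise observed values and change from baseline by visit and product, and label these summaries exploratory because their definitions are set late.
2. Apply the sustained-improvement rule only to tests for which the parent studies supply test-retest data. The photoaversion videos may stay unanalysed.
3. For any test that stays out, restate endpoint 1 and its conclusion as improvement in acuity, contrast sensitivity or reading speed only. State in section 4 the reason for the exclusion and whether outcome data had been seen when it was decided.
4. If the database is already locked, record the same statements in the clinical study report, as SAP section 1 provides for deviations.

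The cost is a summary variable to define for each restored test, some extra descriptive outputs, and self-reported data from unmasked participants that must be read as such. The protocol already schedules these tests, so no new assessment is needed. Step 3 alone would remove the mismatch at the cost of a few sentences, but would leave the possible photoaversion benefit unexamined.
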